#### B. Endpoints

The primary endpoints for the trial will be safety, tolerability, and PSA complete response (PSA CR) rate. A PSA CR will be defined as a serum PSA <0.2 ng/mL, with a confirmatory PSA <0.2 ng/mL at least 4 weeks later, as per PCWG2 recommendations [67]. To qualify as a PSA CR, there must be no evidence of radiographic progression. Patients will come off study at the time of appearance of metastatic disease (radiographic progression), at the time of undue toxicity (as defined below), or at the discretion of the patient and treating physician that other therapies for

prostate cancer are warranted. Patients should be discouraged from discontinuing protocol treatment for PSA rise only. Patients will continue to have blood drawn for immune studies, as per study calendar, up to one year after screening, even if off study prior to that time.

All subjects will undergo radiographic imaging (CT of abdomen and pelvis and bone scan) prior to treatment, and at 6-month intervals (or as clinically indicated). The appearance of lesions consistent with metastatic disease will be used to define radiographic progression, and from these the 2-year metastatic progression-free survival will be calculated for each treatment arm, as well as the median progression-free survival. NOTE: Lesions detected by F-NaF-PET/CT or other advanced imaging (such as NaF-PET/CT, choline PET/CT, fluviclovine, or PSMA PET scans) only will not be used to define metastatic disease or disease progression. MRI imaging may substitute for CT, but the same type of imaging must be used to determine eligibility and progression. RECIST 1.1 criteria will be used to define metastatic disease (appearance of a visceral lesion > 10 mm by CT or MRI, lymph node > 15 mm in short axis, or appearance of new lesions on bone scan consistent with metastatic disease). The 2-year metastasis-free survival will be determined by investigator review of radiographic studies (CT/MRI and bone scintigraphy) performed 2 years after study initiation in subjects who have not already met criteria for radiographic progression.

PSA doubling times will be calculated from four available serum PSA values obtained up to one year from the same clinical laboratory prior to study enrollment, up to and including the baseline value, and used to determine a pre-treatment PSA doubling time (PSADT). Similarly, a post-treatment doubling time will be calculated from:

- (1) All PSA values obtained from the same clinical laboratory using the same PSA assay beginning with the PSA value at day 1 (week 0) and continuing until the end-of study (or month 24) value (PSADT0-24).
- (2) All PSA values obtained from the same clinical laboratory using the same PSA assay beginning with the PSA value at day 85 (month 3) to the day 253 (month 9) value (PSADT3-9).

These time points for PSADT assessment were chosen to correspond to those being obtained in a randomized phase 2 trial using the pTVG-HP vaccine alone (NCT01341652).

## **7. Definition and Management of Limiting Toxicities and Adverse Events**

A treatment-limiting toxicity will be defined as any Grade 3 or greater toxicity (using the NCI Common Terminology Criteria version 4), or a specific Grade 2 event as described below that affects agent dosing, with an attribution of at least possibly related to the study or treatment procedures, and occurring between the pre-study visit and within one month of the final study vaccine treatment or within 90 days of the last treatment with nivolumab (whichever is later). If a patient develops Grade 3 toxicity with an attribution of at least possibly related to nivolumab and unlikely related (or unrelated) to pTVG-HP, the nivolumab treatment will be held until the toxicity resolves to Grade 1 or less, with the vaccine schedule continuing as per protocol. In general, if a patient develops a second Grade 3 event (or any Grade 4 event) believed to be at least possibly

due to nivolumab, but unlikely related (or unrelated) to pTVG-HP vaccine, no further nivolumab treatments will be given. However, Grade 3 or 4 events that would not limit continued treatment or intervention (e.g. lymphopenia or asymptomatic elevations of amylase or lipase) will not require holding the dosing or discontinuation of nivolumab. The specific management for nivolumab-associated adverse events (and the indications for delaying or discontinuing nivolumab treatment) are shown in the table below. In the absence of adverse events attributed to DNA vaccine, the patient will continue with DNA vaccine administration only as per protocol. However, if a patient develops a Grade 3 toxicity with an attribution of at least possibly related to pTVG-HP vaccine, both vaccine and nivolumab treatment will be held until the toxicity resolves to Grade 1 or less. If a patient develops a second Grade 3 event (or any Grade 4 event) believed at least possibly related to pTVG-HP vaccine, no further treatments (nivolumab or vaccine) will be given. The patient will remain on study, however, with collection of radiographic and laboratory data as per protocol. The rationale for these modifications is that patients could continue to benefit in terms of anti-tumor response and this could in fact be related to the development of other autoimmune toxicities, and patients who have toxicity from nivolumab could still potentially benefit from continued DNA vaccination. While rare overall, autoimmune events observed following nivolumab treatment of patients with melanoma typically resolved and did not necessarily lead to discontinuation of treatment.

AEs associated with nivolumab exposure may represent an immunologic etiology. These immune-related AEs (irAEs) may occur shortly after the first dose or several months after the last dose of nivolumab treatment and may affect more than one body system simultaneously. Therefore, early recognition and initiation of treatment is critical to reduce complications. Based on existing clinical study data, most irAEs were reversible and could be managed with interruptions of nivolumab, administration of corticosteroids and/or other supportive care. For suspected irAEs, ensure adequate evaluation to confirm etiology or exclude other causes. Additional procedures or tests such as bronchoscopy, endoscopy, skin biopsy may be included as part of the evaluation. Based on the severity of irAEs, it may be necessary to withhold or permanently discontinue nivolumab and administer corticosteroids. In general, if IV corticosteroids are used, these can be switched to oral dose equivalent (e.g. prednisone), and then tapered, once sustained clinical improvement is observed. Dose modification and toxicity management guidelines for irAEs associated with nivolumab are provided in the following Table:

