**Dose modification and toxicity management guidelines for immune-related AEs associated with nivolumab**

Immune-related AEs	Toxicity grade or conditions (CTCAEv4.0)	Management	Monitor and follow-up
Diarrhea / Colitis	Grade 1 (<4 stools per day over baseline; asymptomatic colitis)	Continue per protocol Symptomatic treatment	Close monitoring for worsening symptoms Educate patient to report worsening immediately If worsens, treat as grade 2 or 3/4
	Grade 2 (4-6 stools per day over baseline; IV fluids required < 24 hours; not interfering with ADL. Colitis:)	Delay nivolumab per protocol Symptomatic treatment	If improves to grade 1, resume nivolumab per protocol  If persists > 5-7 days or recurs: 0.5-1.0 mg/kg/day methylprednisolone or oral equivalent

	abdominal pain, blood in stool		When resolves to grade 1, taper steroids over at least one month, consider prophylactic antibiotics, and resume nivolumab  If worsens or persists >3-5 days with oral steroids, treat as grade 3/4
	Grade 3-4 ( $\geq 7$ stools per day over baseline; IV fluids $\geq 24$ hours; interfering with ADL. Colitis: severe abdominal pain, medical intervention required, peritoneal signs. Grade 4: life threatening, or perforation	Discontinue nivolumab  1.0 to 2.0 mg/kg/day methylprednisolone or IV other corticosteroid equivalent  Add prophylactic antibiotics for opportunistic infections  Consider lower endoscopy	If improves, continue steroids to grade 1, then taper over at least one month  If persists > 3-5 days, or recurs after improvement: Add infliximab 5 mg/kg (if no contraindication). Note: infliximab should not be used if perforation or sepsis
Renal	Grade 1 (creatinine $>$ ULN and $>$ baseline, but $\leq 1.5 \times$ baseline)	Continue as per protocol  Monitor creatinine weekly	If returns to baseline, monitor creatinine as per protocol  If worsens, treat as grade 2 or 3/4
	Grade 2-3 (creatinine $>1.5 \times$ baseline and $\leq 6 \times$ ULN)	Delay nivolumab  Monitor creatinine daily  0.5 to 1.0 mg/kg/day methylprednisolone or oral equivalent  Consider bx or renal consult	If returns to grade 1: Taper steroids over at least 1 month, consider prophylactic antibiotics, resume nivolumab and creatinine monitoring as per protocol  If elevation persists > 7 days: Treat as grade 4

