	Grade 4 (creatinine $> 6 \times$ ULN)	Discontinue nivolumab  Monitor creatinine daily  1.0 to 2.0 mg/kg/day methylprednisolone or IV other corticosteroid equivalent  Consult nephrologist, consider biopsy	If returns to grade 1: Taper steroids over at least 1 month, and add prophylactic antibiotics for opportunistic infections
Pneumonitis	Grade 1 (radiographic changes only)	Consider delay of nivolumab  Monitor symptoms every 2-3 days  Consider pulmonary and ID consults	Reimage at least every 3 weeks  If worsens, treat as grade 2 or 3/4
	Grade 2 (mild to moderate new symptoms)	Delay nivolumab  Pulmonary and ID consults	Re-image every 1-3 days  If improves:

		
Monitor symptoms daily, possible hospitalization
 
1.0 mg/kg/day methylprednisolone or oral equivalent
 
Consider bronchoscopy, lung biopsy
	
When symptoms improve to near baseline, taper steroids over at least 1 month, and then resume nivolumab as per protocol. Consider prophylactic antibiotics
 
If not improved after 2 weeks or worsening: Treat as grade 3/4

	Grade 3/4 (severe new symptoms, new/worsening hypoxia; life threatening)	
Discontinue nivolumab
 
Hospitalize
 
Pulmonary and ID consults
 
2-4 mg/kg/day methylprednisolone or IV equivalent
 
Add prophylactic antibiotics for opportunistic infections
 
Consider bronchoscopy, lung biopsy
	
If improves to baseline: Taper steroids over at least 6 weeks
 
If not improving after 48 hours or worsening: Add additional immunosuppression

Hepatic / Liver Function Test Elevation	Grade 1 (AST or ALT > ULN to 3x ULN and/or total bili > ULN to 1.5x ULN)	Continue nivolumab as per protocol	
Continue LFT monitoring as per protocol
 
If worsens, treat as grade 2 or 3/4

	Grade 2 (AST or ALT >3.0 to $\leq$ 5x ULN and/or total bili > 1.5 to $\leq$ 3x ULN)	
Delay nivolumab
 
Increase monitoring LFTs to every 3 days
	
If returns to baseline: Resume routine monitoring and resume nivolumab
 
If elevation persist > 5-7 days or worsens: 0.5 – 1 mg/kg/day methylprednisolone or oral equivalent and when LFT returns to grade 1 or baseline, taper steroids over at least 1 month, consider prophylactic antibiotics, and resume nivolumab as per protocol

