	Grade 3/4 (AST or ALT > 5x ULN or total bili > 3x ULN)	
Discontinue nivolumab
 
NOTE: May be delayed rather than discontinued if AST/ALT <math>\leq</math> 8xULN or total bili <math>\leq</math> 5x ULN
 
Increase LFT monitoring to every 1-2 days
 
1.0 to 2.0 mg/kg/day methylprednisolone or IV equivalent
 
NOTE: 2 mg/kg/day recommended for grade 4
 
Add prophylactic antibiotics for opportunistic infections
 
Consult gastroenterologist
	
If returns to grade 2: Taper steroids over at least 1 month
 
If does not improve in >3-5 days, worsens, or rebounds: Add mycophenolate mofetil 1 g bid If no response within an additional 3-5 days, consider other immunosuppressants

Endocrinopathies	Asymptomatic TSH elevation	Continue nivolumab as per protocol	If TSH < 0.5 x LLN or > 2x ULN, or consistently out of range in 2 measurements, include free T4 at subsequent cycles and treat as clinically indicated. Consider endocrinology consult
	Symptomatic endocrinopathy	
Evaluate endocrine function Consider pituitary scan (MRI)
 
Grade 3 drug-related endocrinopathies, adequately controlled with only physiologic hormone replacement do not require discontinuation. Adrenal insufficiency requires discontinuation regardless of control with hormone replacement.
 
Grade 4 drug-related endocrinopathy AEs, such as, hyper- or hypothyroidism, or glucose intolerance, that resolve or are adequately controlled with physiologic hormone replacement (corticosteroids, thyroid hormones) or glucose-controlling agents, respectively, may not require discontinuation.
 
Grade 4 drug-related adrenal insufficiency or hypophysitis requires discontinuation regardless of control with hormone replacement.
	
	Suspicion of adrenal crisis (e.g. severe dehydration, hypotension, shock out of proportion to current illness)	
Discontinue nivolumab for any drug-related grade 3 or 4 adrenal insufficiency
 
Rule out sepsis
 
Stress dose of IV steroids with mineralocorticoid activity
 
IV fluids
 
Consult endocrinologist
	

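### Section 7 only holds nivolumab after a first Grade 3 event where its own tables discontinue it, and no sentence says which governs

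*Combined protocol and SAP*

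**What the plan says.** Section 7 manages nivolumab through two attribution rules in the text, then two tables.

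- **Nivolumab-only rule.** For a Grade 3 event possibly due to nivolumab but unlikely related or unrelated to pTVG-HP, nivolumab is held until Grade 1 or less and vaccination continues. A second Grade 3 or any Grade 4 event ends nivolumab, as a general rule.
- **Pointer.** The text then says: "The specific management for nivolumab-associated adverse events (and the indications for delaying or discontinuing nivolumab treatment) are shown in the table below".
- **Vaccine rule.** After the pointer, and introduced as a contrast, comes the rule for a Grade 3 event at least possibly related to pTVG-HP: "both vaccine and nivolumab treatment will be held until the toxicity resolves to Grade 1 or less". For a second Grade 3 or any Grade 4 event "believed at least possibly related to pTVG-HP vaccine, no further treatments (nivolumab or vaccine) will be given". The trigger looks only at attribution to the vaccine, so an event possibly related to both agents falls here.
- **Rationale.** "The rationale for these modifications is that patients could continue to benefit in terms of anti-tumor response".
- **Tables.** One table covers immune-related events and a separate one covers infusion reactions. Each gives nivolumab instructions by event and grade. The hepatic row carries an exception that begins "May be delayed rather than discontinued if AST/ALT".

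**The concern.** A hold until Grade 1 is a temporary instruction; a discontinuation is not. For several first Grade 3 events the text gives the former and the tables the latter, and no sentence ranks them. A site that treats the text as controlling could restart nivolumab after a toxicity that the protocol's own tables treat as ending it.

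Joint attribution is foreseeable. Section 13.A calls it conceivable that the combination produces more autoimmune events than either agent alone, and both agents are given at the same visits. The trial is multi-institution, so sites may read the text differently. Safety and tolerability form a primary objective.

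**Working it through.** **Step 1. Compare the instructions at a first Grade 3 event.** Both narrative rules say the same thing: hold nivolumab to Grade 1 or less.

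| Event group | Table instruction for nivolumab | Differs from the hold? |
|---|---|---|
| Diarrhea/colitis | Discontinue | Yes |
| Pneumonitis | Discontinue | Yes |
| Neurologic | Discontinue | Yes |
| Infusion reaction (second table) | Permanently discontinue | Yes |
| Endocrinopathy | Discontinue for adrenal insufficiency; not required if others are controlled by physiologic hormone replacement | In part |
| Hepatic | Discontinue, with optional delay if AST/ALT ≤ 8x ULN or total bilirubin ≤ 5x ULN | In part |
| Skin | Delay or discontinue; permanent discontinuation for SJS/TEN | In part |
| Renal | Delay; if elevation lasts over 7 days, treat as Grade 4, which is discontinue | In part |
| All other immune-related | Delay | No |

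Four groups differ in full and four in part: 4 + 4 = 8 of 9.

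**Step 2. Compare at Grade 4.** For any Grade 4 event possibly related to pTVG-HP, the vaccine rule ends both agents. The endocrine row says controlled Grade 4 events may not require discontinuation, except adrenal insufficiency and hypophysitis. The skin row covers Grades 3 and 4 together and allows delay and resumption, SJS/TEN excepted. Here the text is the stricter source.

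**Step 3. Look for precedence.** The pointer is the only linking sentence. It directly follows the nivolumab-only provisions, so it goes some way to reconciling them with the immune-related table. It precedes the vaccine rule, which names nivolumab and does not mention the tables. It refers to one table, while infusion reactions sit in another.

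**Step 4. Size for one patient.**

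- Schedule (Section 6): 240 mg every 2 weeks x 6 (weeks 0 to 10), then every 4 weeks x 9 (weeks 12, 16, ..., 44); 6 + 9 = 15 doses.
- Event just after the week 10 dose: 15 − 6 = 9 doses remain.
- Assumptions: recovery to Grade 1 takes t = 1 to 6 weeks; dosing restarts at the next scheduled visit; missed doses are not made up; visit windows are ignored.
- Restart is the first scheduled dose at or after week 10 + t.
  - t = 1 to 2: weeks 11 to 12, restart week 12, 0 missed, 9 given (9 × 240 = 2,160 mg).
  - t = 3 to 6: weeks 13 to 16, restart week 16, 1 missed, 8 given (8 × 240 = 1,920 mg).
- Table discontinuation: 0 further doses.

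**Sensitivity.** The narrative rule does not require a steroid taper before restart. The tables do specify one: for colitis, "If improves, continue steroids to grade 1, then taper over at least one month"; for pneumonitis, "Taper steroids over at least 6 weeks". If a site restarted only after that taper, colitis (30 days) with t = 1 gives week 15.3 and 8 doses, and t = 6 gives week 20.3 and 6 doses. Pneumonitis (42 days) with t = 1 gives week 17 and 7 doses, and t = 6 gives week 22 and 6 doses. All remain far from 0.

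**The case against.** The strongest reply is that the document already answers the question. The pointer places the indications for delaying or discontinuing nivolumab in the table, and event-specific instructions naturally override general ones. The vaccine rule never says that nivolumab must resume, so a site that discontinues complies with both texts. The rationale ends by naming continued vaccination, not continued nivolumab, for patients with nivolumab toxicity. Oversight is also real: Grade 3 pneumonitis calls for hospitalization, which makes it an SAE with 24-hour reporting and DSMC chair review (Section 12), and adverse events are reviewed weekly (Section 14.B).

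Much of this stands. Discontinuing is the more natural reading for a careful site, especially where the event is attributed to nivolumab alone. It does not close the gap. A hold until a stated grade ordinarily implies resumption, the vaccine rule comes after the pointer without deferring to it, and the tables are introduced as guidelines while the rule is stated as what will happen. Review may catch a restart but supplies no rule, and a laboratory-only Grade 3 hepatic event need not be an SAE.

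A reader might infer that the protocol requires re-exposure, or that the text is always the laxer source. Neither is supported: restart is permitted on one reading only, and at Grade 4 the text is stricter. Nor do the documents support confining the problem to events attributed to both agents, since the nivolumab-only rule has the same hold wording.

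**Conclusion.** The mismatch is real and should be corrected. At a first Grade 3 event the text and tables differ, wholly or in part, in 8 of 9 event groups; at Grade 4 they differ in the opposite direction for controlled endocrinopathies and skin events. Precedence is suggested by the pointer but not stated.

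In the worked case the two readings differ by 8 to 9 nivolumab doses (1,920 to 2,160 mg). That rests on the assumed 1 to 6 week recovery, the chosen event time and restart at Grade 1. The documents give no rate for joint attribution or for these events in this population, so the number of patients affected cannot be derived. This is a patient-safety drafting conflict; a reader might infer a bias in the PSA complete response analysis, but nothing in the documents establishes one.

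**What to change.** In Section 7, directly after the sentence ending "believed at least possibly related to pTVG-HP vaccine, no further treatments (nivolumab or vaccine) will be given", insert:

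> Any nivolumab discontinuation required by the immune-related AE table or the infusion-reaction table applies whatever the attribution to pTVG-HP and overrides the hold-until-Grade-1 rules above; where the text and a table differ for an event at least possibly related to pTVG-HP, the stricter nivolumab instruction applies, and pTVG-HP dosing follows the text above.

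The first clause settles the first Grade 3 cases under both narrative rules. The second settles Grade 4 events possibly related to the vaccine. After a listed first Grade 3 event, nivolumab stops. pTVG-HP is held to Grade 1 or less and may then continue alone if the event is possibly related to it; otherwise it continues on schedule.

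Cost: a protocol amendment with UW IRB approval before use and participating-site approvals. Because the change concerns adverse events that could affect subject safety, Section 14.D also calls for a revised consent form, which enrolled subjects would be asked to sign. Sample size, endpoints, visits and analysis do not change.

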R. Week 84 visit (84 +/- 14 days after week 72 visit)

1. Physical examination, including vital signs, symptoms assessment, and ECOG performance score
2. Blood draw CBC, chemistry panel, PSA and PAP.

S. Week 96 visit (84 +/- 14 days after week 72 visit) – END OF STUDY

1. Physical examination, including vital signs, symptoms assessment, and ECOG performance score
2. Blood draw CBC, chemistry panel, PSA and PAP.
3. CT scan of abdomen and pelvis, and bone scan (can be performed +/- 7 days of this visit)

T. 28-Day Follow Up Visit (28 +/- 7 days after Off-study date, if prior to week 48)

Patients will come off study at the time of disease progression, undue toxicity, or at the discretion of the patient and/or treating physician that it is not in the interest of the patient to continue treatment. A separate follow-up visit is not required for patients completing the week 48 evaluation, however for patients coming off study prior to week 48, 28-day follow up visit will include the following:

1. Physical examination, symptoms assessment, and ECOG performance score.
2. Blood draw for CBC, chemistry panel, serum PSA and PAP
3. IF NOT ALREADY COLLECTED WITHIN PREVIOUS 60 DAYS: 10 ml peripheral blood (red-top tubes) for sera to evaluate antibody responses, and 100 ml peripheral blood (green-top heparinized tubes) for T-cell response evaluation

U. Long-term Follow-Up

Subjects will be contacted by telephone (if not already being seen in clinic) annually for 2 years following the last DNA vaccination to collect clinical information to identify any potential long-term risks. This information has been requested by FDA for all gene delivery trials to assess potential long-term risks. The specific information to be collected annually will include:

- Date of contact
- Current medications
- Hospitalizations (dates and reasons for hospital admission)

- Stage of prostate cancer, treatments for prostate cancer, and recent serum PSA level
- New cancer diagnoses
- New autoimmune disorders
- New hematologic or neurologic disorders
- Other new medical diagnoses
- Date of death if patient deceased

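### Sections 6.B, 7 and 8.T disagree on whether patients stopped for toxicity stay on study, so the PSA values and scans behind the primary response and 2-year metastasis-free survival may not be scheduled for them

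*Combined protocol and SAP*

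**What the plan says.** Section 7 covers permanent stopping for toxicity. After a second Grade 3 event, or any Grade 4 event, at least possibly related to the vaccine, "no further treatments (nivolumab or vaccine) will be given". The next sentence reads "The patient will remain on study, however, with collection of radiographic and laboratory data as per protocol". Patients who stop nivolumab alone, for events not attributed to the vaccine, carry on with the vaccine.

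Section 6.B says otherwise: "Patients will come off study at the time of appearance of metastatic disease (radiographic progression), at the time of undue toxicity". It adds that undue toxicity is defined later, but no later section defines it. Section 7 defines only a treatment-limiting toxicity. Section 8.T repeats the rule: "Patients will come off study at the time of disease progression, undue toxicity, or at the discretion of the patient and/or treating physician". It continues that "for patients coming off study prior to week 48, 28-day follow up visit will include the following", and the list has a physical examination, "Blood draw for CBC, chemistry panel, serum PSA and PAP", and immune-study blood if none was taken recently. No CT or bone scan is listed.

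Two kinds of follow-up continue after a patient leaves. Section 6.B keeps immune-study blood draws up to one year after screening. Section 8.U has annual contact for 2 years after the last vaccination, which records disease stage, cancer treatments and a recent PSA.

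Section 6.B defines a PSA complete response (CR) as two values below 0.2 ng/mL at least 4 weeks apart, with no radiographic progression. Two-year metastasis-free survival rests on CT or MRI and bone scans.

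**The concern.** A site that has stopped both agents for toxicity finds two instructions with different data collection. Under Section 7 the PSA and imaging calendar runs on. Under Sections 6.B and 8.T it ends, apart from one visit.

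The data that would stop are those behind the primary efficacy endpoint and the first secondary endpoint. The final decision needs only 5 CRs among 41 patients, so one or two missed CRs can change it. The analysis text in Section 10.D does not say how patients who leave for toxicity are counted for the CR rate or censored for metastasis-free survival. The more detailed analysis plan promised there could settle the counting, but it could not recover PSA values and scans that were never taken.

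The loss might also be related to response. Section 7 gives a possible link between anti-tumor response and autoimmune toxicity as part of its reason for the treatment modifications.

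**Working it through.** **1. What is scheduled after a stop of both agents before week 48**

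| Item | Section 7 | Sections 6.B and 8.T |
|---|---|---|
| Status | On study | Off study |
| PSA | Per calendar | One draw, 28 ± 7 days after the off-study date |
| CT and bone scan | Per calendar | None listed |
| Later contact | Calendar, then 8.U | Immune blood; 8.U annual contact, no test scheduled |

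**2. Which responses are at risk on the 8.T path**

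Let g be the days from the last low on-study PSA to the off-study date. The 28-day visit falls on days 21 to 35, so the gap between the two PSA draws is g + 21 to g + 35 days.

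- If g is 7 or more, the gap is at least 28 days and the visit can confirm the response.
- If g is below 7, an early visit gives a gap under 28 days and cannot confirm it. With g = 0 this applies to visits on days 21 to 27.
- A response first seen at the 28-day visit, or later, has no scheduled second value.
- A response confirmed before the stop is kept.

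**3. The plan's own power figure**

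Inputs are from Section 10.C (21 patients in stage 1, stop at 1 CR or fewer, 20 more in stage 2) and 10.D (at least 5 CRs of 41 to reject). With X1 and X2 the stage counts:

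- Early stop = P(X1 ≤ 1)
- Power = Σ over x ≥ 2 of P(X1 = x) × P(X2 ≥ 5 − x)

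At a true rate of 0.20:

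- Early stop = 0.8^21 + 21 × 0.2 × 0.8^20 = 0.0092 + 0.0484 = 0.0576
- Power = 0.1211 × 0.7939 + 0.1917 × 0.9308 + 0.2156 × 0.9885 + 0.4140 = 0.902, where 0.4140 is P(X1 ≥ 5)

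The plan states 6% and 90%, so both reproduce.

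**4. Effect of lost responses**

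Let L be the share of CRs that go unobserved. The documents give no value, so L is an assumption. Lost CRs are counted as non-responses, which the documents do not state either. The observed rate is 0.20 × (1 − L), put through the same formulas.

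| L | Observed rate | Power | Wrong stage-1 stop |
|---|---|---|---|
| 0 | 20.0% | 90.2% | 5.8% |
| 2% | 19.6% | 89.2% | 6.3% |
| 5% | 19.0% | 87.6% | 7.1% |
| 10% | 18.0% | 84.4% | 8.7% |
| 20% | 16.0% | 76.0% | 12.8% |

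L is a share of responses, not of patients. If patients who leave respond as often as the others, L is the share leaving times the share of their CRs missed. For example, 10% leaving with half their CRs missed gives L = 5% and power 87.6%. If those who leave respond more often, L is larger for the same number leaving.

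**The case against.** The passages can be read together. Section 6.B points forward for its definition, and Section 7 is the specific rule that follows. The 8.T sentence ends by speaking of continuing treatment, so off study there may mean off treatment. Section 6.B also plans scans every 6 months for all subjects, and at 2 years for those who have not progressed, which fits the Section 7 reading. This shows what was probably intended. It does not remove the conflict, because 8.T attaches its own shorter visit list to coming off study.

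A reader might go further than the documents allow in four ways.

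- **That responses and metastases in these patients would never be observed.** Annual contact under 8.U records stage and a recent PSA, so some would surface, though not through scheduled tests.
- **That every unconfirmed response is lost.** The 28-day PSA can confirm one first seen on study if the draws are at least 4 weeks apart.
- **That everyone stopped for toxicity is affected.** The sentence keeping patients on study follows the vaccine-related rule that ends both agents; patients who stop only nivolumab continue the vaccine.
- **That losses of 10% to 20% are to be expected.** Section 6.A anticipates no vaccine-attributable events above Grade 2 and reports no Grade 4 events among 26 patients given this vaccine with pembrolizumab. Neither figure gives the stopping rate for this combination, but they are reason to include low losses in the range.

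The remark linking response to autoimmune toxicity is a rationale, not evidence that responders would be lost preferentially.

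**Conclusion.** The contradiction is real, and nothing elsewhere in the document resolves it. Following Section 8.T would drop scheduled PSA and imaging in patients whom Section 7 keeps under observation, and so could bias the primary CR rate downward and leave metastasis-free survival incompletely ascertained.

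The size depends on an unknown share of lost CRs. Up to 5%, the power loss is under 3 points (90.2% to 87.6%). At 20% it is about 14 points (90.2% to 76.0%), and the chance of wrongly stopping after stage 1 rises from 5.8% to 12.8%. These figures assume a true rate of 20% and lost CRs counted as non-responses; they illustrate the effect and do not forecast it. The point should be corrected because the remedy is cheap and Section 7 already contains it.

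**What to change.** Reconcile Sections 6.B, 7 and 8.T. Define off treatment and off study as separate states, and either define undue toxicity or replace it with a defined term. State that patients who stop treatment for toxicity continue PSA and CT/bone scan per the study calendar to week 96, as Section 7 already requires, unless consent is withdrawn or metastasis appears. Limit the single 28-day visit to patients who truly leave the study.

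The cost is wording in three sections plus follow-up tests that Section 7 already calls for. The change concerns data collection only; which toxicities end treatment is not addressed. A rule on counting responses after other anticancer therapy would be a separate choice, which this contradiction does not require.
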